The demonstration of efficacy in AML motivates the exploration of ribavirin in other malignancies. Head and neck cancer is an obvious choice due to clinical and preclinical data demonstrating the eIF4E appears to play a significant role (20, 21, 52). Additionally, ribavirin has potent antitumor activity against a HNSCC cell line (FaDu) that overexpresses eIF4E. *In vitro*, ribavirin inhibits phosphorylation of Akt and reduces anchorage independent growth of FaDu cells (53). In a xenograft model using FaDu cells, 20 days of treatment with ribavirin yielded a 6-fold reduction in mean tumor volume in treated animals, compared with the control group (45). The hypothesis that this growth inhibition may be mediated by ribavirin's effect of eIF4E is supported by the observation that reduction of eIF4E expression in FaDu cells with antisense RNA also reduces the tumorigenic and angiogenic properties of FaDu cells (21). Taken together, we feel that these observations support a pilot study of ribavirin in head and neck cancer. In order to enrich for patient population that expresses the eIF4E target, the study is limited to never smokers (or past oligo smokers) with tonsillar squamous cell cancer (see Table 1 above).

3.5 Rationale for Tissue Pharmacodynamic Studies

To obtain proof-of-principle regarding the hypothesis that ribavirin is an inhibitor of eIF4E (45, 48, 49), we will compare pre and post treatment tumor levels of phosphorylated eIF4E by immunohistochemistry. Expression of phosphorylated eIF4E is associated with p16 positive tonsil squamous cell carcinoma (24) [see Table 1 herein]. In AML, ribavirin therapy results in decreased levels of eIF4E mRNA and protein (49) [see Figure 1 and Table 2 herein]. eIF4E can function as an oncogene (18), and pharmacodynamic demonstration of downregulation of eIF4E would provide a mechanistic basis for further development of ribavirin in HPV-positive head and neck cancer.

As a secondary endpoint, we will explore if ribavirin alters levels of selected proteins that are regulated by eIF4E at the translational level. In a model system with primary human mammary epithelial cells (HMECs), eIF4E activates p16 and p21 and represses EGFR receptor (17). This eIF4E-induced pattern of expression (high p16, high p21, and low EGFR) seen in HMECs (17) is very similar to the protein expression patterns seen in HPV-positive HNSCC (3, 8, 24). The striking similarities between expression patterns induced by eIF4E in a HMEC model system and the expression patterns in HPV-positive HNSCC prompt exploratory pharmacodynamic assays involving pre and post-treatment tissue in this study. We wish to obtain pilot data to determine if ribavirin impacts expression of p16, p21, and/or EGFR in patient tumors in this study, which could strengthen the hypothesis that ribavirin is an inhibitor eIF4E activity.

We also wish to explore if ribavirin treatment effects the expression of viral oncoproteins E6 and E7. HPV-16 uses a single promoter to drive expression of a bicistronic mRNA that encodes E6 and E7. Synthesis of both E6 and E7 from the bicistronic transcript is dependent on an m⁷G cap structure on the 5'end of the mRNA (54). In view of the hypothesis that ribavirin may interfere with translation of cap-dependent mRNA transcripts (43-45), we wish to obtain pilot data regarding whether inhibition of production of E6 and E7 might be a mechanism of action for ribavirin in HPV-positive tonsil squamous cell carcinoma.

3.6 Summary and Future directions

In this study, up to 7 evaluable subjects will be treated with ribavirin for 14 days to evaluate the pharmacodynamic effects of ribavirin in HPV-positive oropharynx SCC. We feel that 14 days is adequate to demonstrate the pharmacodynamic effects of ribavirin because (1) Ribavirin pharmacology is characterized by rapid absorption and rapid distribution (Section 5.1); (2) Ribavirin often causes mild anemia within 2 weeks, consistent with rapid onset clinical activity of the drug (61); (3) For other targeted therapies with well-defined mechanisms of action in oncology, pharmacodynamic activity is evident in 15 days or less (62, 63); (4) In the pilot study of ribavirin in AML, the first response assessment occurred at 14 days (49).

Squamous tumors of tonsil and base of tongue, both oropharynx subsites, share the same underlying molecular pathology in which HPV figures prominently in the development of malignancy (1). Primary surgical resection or primary radiation +/- chemotherapy (concurrent or sequential) may be offered to patients with either tonsil or base of tongue SCC. Because HPV-driven pathology is a shared characteristic of SCC at both of these subsites, we feel that it is appropriate to include both tonsil and base of tongue SCC in this study.

MEMORIAL SLOAN-KETTERING CANCER CENTER IRB PROTOCOL

IRB#: 10-218 A(8)

If the pilot data from this study is consistent with the hypothesis that ribavirin is an inhibitor or eIF4E, we would pursue further clinical studies of ribavirin in head and neck cancer. In view of the reported supra-additive effects of cisplatin + eIF4E inhibition against HNSCC cancer cell lines (22), we would consider a phase I/II study of ribavirin + low dose weekly cisplatin + external beam radiation therapy for patients with stage III/IVB HPV-positive HNSCC. The low-dose cisplatin regimen would likely be better tolerated than the current standard high-dose cisplatin regimens (64, 65). We would also wish to consider a phase I/II study of ribavirin + cisplatin + docetaxel as induction chemotherapy for patients with stage III/IVB HPV-positive HNSCC. The use of 2 cytotoxic agents in this experimental induction regimen would likely be better tolerated than the current standard induction chemotherapy in HNSCC which is three cytotoxic agents (cisplatin, docetaxel, 5-fluorouracil) (66). Another study option might be developed for patients who undergo primary surgery for head and neck cancer. In view of the report that expression of eIF4E in histologically tumor free margins is associated with increased risk of recurrence (20), a post-operative treatment regimen incorporating ribavirin would be an attractive study concept. Each of the study concepts outlined above would provide the opportunity to obtain adequate tumor tissue for correlative studies to further analyze the mechanistic effects of ribavirin. Finally, in view of the worldwide burden of cervical carcinoma which is also characterized by elevated eIF4E expression (31), these findings potentially could have implications beyond head and neck cancer clinical research.

4.1 OVERVIEW OF STUDY DESIGN/INTERVENTION

4.2 Design

This will be a single institution non-randomized study for patients with tonsil and/or base of tongue squamous cell cancer. This is a pilot study to obtain pharmacodynamic data regarding the effects of ribavirin on tonsil and/or base of tongue squamous cell cancer. After patients provide informed consent, eIF4E expression in tumors will be measured by immunohistochemistry. Those patients with tumors that express eIF4E $\geq 30\%$ will be deemed eligible for the study and will self-administer ribavirin for approximately 14 days. The primary endpoint is to explore if ribavirin decreases tumor expression of phosphorylated eIF4E among patients with tonsil and/or base of tongue squamous cell carcinoma. Immunohistochemistry will be performed on pre-treatment pathology samples (e.g. diagnostic biopsy), as well as on the post-treatment pathology samples (e.g. definitive surgery or research biopsy), to describe the effects of ribavirin treatment on the expression of phosphorylated eIF4E.

4.3 Intervention

Patients will self-administer ribavirin for approximately 14 days prior to surgery. Patients will undergo safety assessments with clinic visits and routine laboratory studies at least once per week. On approximately day 15, patients will undergo planned surgical resection or research biopsy. Patients will be considered done with treatment at time of surgery or research biopsy. Post-operative (or post research biopsy) management will be according to standards of care off protocol.

For those patients who undergo research biopsy, this will be performed in the clinics of the Head and Neck Disease Management Team. Research biopsy will be performed on easily accessible lesions. The phrase "easily accessible tumor" designates tumors that may be biopsied in an office setting with minimal risk of complication and discomfort to the patient. Common techniques for office biopsy include fine needle aspirate of malignant neck node, or forceps cut biopsy of primary tumor (with local anesthetic). The method used for research biopsy in the clinic is at the discretion of the investigator.

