6.0 CRITERIA FOR SUBJECT ELIGIBILITY

6.1 Subject Inclusion Criteria

1. Prior diagnostic surgical or core needle biopsy, with confirmation of tonsil and/or base of tongue squamous cell carcinoma that is positive for expression of p16 and phosphorylated eIF4E, as determined by the Department of Pathology at MSKCC. The biopsy may be either of the tonsil, base of tongue, and/or an involved neck node. 2 unstained slides and/or tissue block must be available from the initial diagnostic biopsy

Positive expression p16 and phosphorylated eIF4E is defined as $\geq 30\%$ of tumor cells with cytological and/or nuclear staining

2. Age ≥ 18 and ≤ 65 years of age
3. Karnofsky Performance Status ≥ 80
- 4.

Adequate organ function, as follows:

Adequate bone marrow reserve: absolute neutrophil count (ANC) $\geq 1.5 \times 10^9/L$, platelets $\geq 160 \times 10^9/L$, hemoglobin $\geq 12 \text{ g/dL}$

Hepatic: total bilirubin within $1.5 \times$ upper limit of normal (ULN) ; alkaline phosphatase (AP), aspartate transaminase (AST) and alanine transaminase (ALT) $\leq 2.5 \times$ ULN

(Patients with Gilbert's syndrome as the cause of hyperbilirubinemia may be eligible if total bilirubin $\leq 2.5 \times$ UNL)

Renal: Serum creatinine $\leq 1.3 \text{ mg/dL}$. Patients with serum creatinine $> 1.3 \text{ mg/dL}$ may be eligible if creatinine clearance (CrCl) $\geq 55 \text{ mL/min}$ based on the standard Cockroft and Gault formula.

5. Patients of childbearing potential must have a negative serum pregnancy test within 14 days of treatment. Patients must agree to use a reliable method of birth control during and for 6 months following the last dose of study drug.
6. Ability to swallow oral medication.
7. Non-surgical patients: If primary radiation +/- chemotherapy (concurrent or sequential) is planned, patients must agree to undergo research biopsy after completion of ribavirin treatment.

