9.3 Immunohistochemistry (IHC)

Each formalin-fixed and paraffin-embedded tissue specimen will be processed for IHC, consistent with established methods in our group (70). The time from tumor removal at surgery to formalin fixation should be 2 hours or less.

The avidin-biotin immunoperoxidase technique will be employed. Antigen retrieval with citric acid (0.01%) for 15 minutes under microwave treatment commonly precedes incubation with the primary antibody (usually overnight at 4°C). Primary antibodies to be used include anti-phospho eIF4E^{Ser209} (rabbit polyclonal, Cell Signaling #9741), anti-p16 (mouse IgG, clone E6H4, Dako #K5334), anti-p21 (mouse IgG, clone EA10, Calbiochem #OP64), anti-EGFR (mouse IgG, clone 31G7, Ventana #28-005), anti-HPV16 E6 (mouse IgG, clone C1P5, Santa Cruz #sc-460), and anti-E7 (mouse IgG, clone 8C9, Invitrogen #28-0006). Diaminobenzidine will be utilized as the final chromogen and hematoxylin will provide the nuclear counterstain.

If limited tumor tissue is available, the top priority immunostain will be phosphorylated eIF4E.

If sufficient tissue is available, exploratory analysis of additional biomarkers may be performed. For example, if immunohistochemistry does not provide definitive data regarding levels of E6, E7, and p53, expression may be explored with RT PCR using established methods (71, 72).

Technical difficulty or inability to obtain results with certain antibodies or samples will not be considered a protocol violation.

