10.1 EVALUATION DURING TREATMENT/INTERVENTION

10.2 Description of Evaluations

Patients will be provided with a pill diary at the start of treatment (Appendix A), and will be required to bring a updated pill diary to each clinic visit. If patients miss any doses of ribavirin, this will not be considered a protocol violation but the investigator retains the discretion to remove patients from study for non-compliance.

Every attempt will be made for patients to have clinic visits and laboratory tests on the indicated dates. However, dates may need to be altered for medical or personal or logistical reasons. Clinic visits and laboratory studies may occur 3 days before or 3 days after the scheduled date, if need be. Additional clinical visits and laboratory studies may be scheduled if clinically necessary, per investigator discretion.

- On Day 1, routine laboratory studies are obtained: complete blood cell count and comprehensive metabolic panel. Patients undergo history and physical.
- Days 1 – 14, approximately: ribavirin 800 mg/day in divided doses, 400 mg q AM and 400 mg q PM. Typically, this will be administered as two 200 mg tablets qAM, and two 200 mg tablets qPM. Use of one 400 mg tablet (instead of two 200 mg tablets) is also allowed, at the discretion of the investigator.
- On Day 8, Routine laboratory studies are obtained: complete blood cell count and comprehensive metabolic panel. Patients undergo history and physical.
- Day 15 (approximately): Surgical plan is resection or research biopsy of the tonsil and/or base of tongue squamous cell carcinoma, possibly with neck dissection at the discretion of the surgeon. Patients will be considered done with treatment at time of surgery or research biopsy. As such, the surgical or biopsy procedure is considered off-protocol, and the surgery or research biopsy will be performed at the discretion of the investigator. The protocol provides no guidance nor places any restrictions regarding surgical management.

While every attempt will be made to schedule surgery or research biopsy on Day 15, the exact timing of surgery or research biopsy will be at the discretion of the surgeon. No ribavirin will be given after surgery or research biopsy.

- Post-operative (or post research biopsy) management will be per standard of care, off protocol.

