14.0 BIOSTATISTICS

The primary endpoint of this pilot study is to explore if ribavirin therapy for 2 weeks decreases tumor expression of phosphorylated eIF4E among patients with tonsillar and/or base of tongue squamous cell carcinomas that expresses phosphorylated eIF4E.

Decision Rule: We would consider ribavirin to be interesting for further study in this patient population if we observe at least 4 patients (among 7) in which positive baseline expression of phosphorylated eIF4E becomes negative after ribavirin treatment.

Positive phosphorylated eIF4E overexpression is defined as $\geq 30\%$ of cells with cytoplasmic and/or nuclear staining by IHC (19, 24). With this 30% cutoff, the probabilities of observing at least 4 patients with negative post-treatment eIF4E expression among the 7 patients included in the study are listed below:

True probability that ribavirin inhibits eIF4E expression	Probability of observing the inhibition in at least 4 of the 7 patients
.40	.29
.50	.52
.60	.71
.70	.87
.80	.97

For each of the patients tested, we will tabulate pretreatment and posttreatment tumor expression of phosphorylated eIF4E, of molecules that are regulated by eIF4E (p16, p21, EGFR), HPV-16 oncoproteins (E6 and E7) and FDG-PET/CT scans, as well as percentage change between pretreatment and posttreatment levels.

Toxicity data (AEs, laboratory data and vital sign data) will be collected and listed individually per patient according to CTCAE version 4.0.

Subjects who take < 10 days of ribavirin prior to surgery (or research biopsy) will be considered inevaluable and will be replaced. The expected accrual rate is 1 to 2 patients per month, so we expect the study to be completed in 4 to 7 months.

Note: If the post-treatment tumor specimen cannot be obtained (eg, technical issues or patient withdraws consent) or if insufficient/inadequate material is available for immunostaining of phosphorylated eIF4E, the subject will be deemed inevaluable and will be replaced. If there is insufficient/inadequate tissue to perform the other immunostains discussed in the secondary aims, this would not be considered a protocol violation and the subject would not need to be replaced as long as the patient was evaluable for the primary endpoint of this pilot study.

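### Baseline and post-treatment specimens need not come from the same site or be of the same type, yet unmatched pairs count in the uncontrolled 4-of-7 rule

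*Combined protocol and SAP*

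**What the plan says.** **Baseline.** Section 6.1 requires a surgical or core needle diagnostic biopsy, so an aspirate cannot qualify a patient. On site it says: "The biopsy may be either of the tonsil, base of tongue, and/or an involved neck node". The tumour must stain positive for phosphorylated eIF4E in at least 30% of cells.

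**Post-treatment.** Around Day 15 the patient has a resection or an office research biopsy. Section 4.3 says "Research biopsy will be performed on easily accessible lesions" and then "Common techniques for office biopsy include fine needle aspirate of malignant neck node, or forceps cut biopsy of primary tumor", and leaves the method to the investigator. Section 10.2 puts it differently: "Surgical plan is resection or research biopsy of the tonsil and/or base of tongue squamous cell carcinoma, possibly with neck dissection". It leaves neck dissection to the surgeon and sets no restrictions on surgical management.

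**Assay.** Section 9.3 says "Each formalin-fixed and paraffin-embedded tissue specimen will be processed for IHC" and gives the phosphorylated eIF4E stain top priority when tissue is short. It gives no separate procedure for aspirates.

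**Decision.** Section 14 calls ribavirin interesting for further study on seeing "at least 4 patients (among 7) in which positive baseline expression of phosphorylated eIF4E becomes negative after ribavirin treatment". Patients are replaced for fewer than 10 days of drug, for a missing post-treatment specimen, or for insufficient or inadequate material. A difference in site or type within a pair is not on that list. Section 4.2 describes a single-institution, non-randomized study, and no untreated group is planned.

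**The concern.** A patient diagnosed on a node core and then resected at the tonsil, or diagnosed on a tonsil biopsy and then sampled by node aspirate, follows the protocol as written and counts in the primary analysis if the stain can be read. In such a pair the change in percent positive cells mixes any drug effect with any difference between primary and node, or between aspirate and tissue.

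Two features of the design make this matter:

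- There is no untreated pair from which the sampling difference could be estimated and subtracted.
- Selection on a positive baseline makes spurious change one-sided. An uninhibited tumour can only stay positive or turn negative, and turning negative is scored as inhibition. A mismatch can also leave a truly inhibited patient reading positive.

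Aspirates can enter only on the post-treatment side, so any aspirate-versus-tissue difference would be systematic, not random. At stake is the one decision rule in the plan, which Section 3.6 links to further clinical studies of ribavirin.

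**Working it through.** **Inputs from the documents (Section 14):** n = 7, success if at least 4 convert, cutoff 30%, and the table of operating characteristics.

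**Input not in the documents:** the rate at which a site or type difference alone moves a specimen across 30%. This is an assumption and is shown as a range.

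**Step 1. Reproduce the plan's table.** P(X ≥ 4) for X ~ Binomial(7, p):

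| True p | Plan | Exact |
|---|---|---|
| .40 | .29 | .290 |
| .50 | .52 | .500 |
| .60 | .71 | .710 |
| .70 | .87 | .874 |
| .80 | .97 | .967 |

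Four of the five rows agree. The .50 row should read .50; that is a separate point and does not affect what follows.

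**Step 2. Misclassification in both directions.** The documents give no direction for a site or type difference, so let a fraction s of uninhibited patients read negative and the same fraction s of inhibited patients read positive. The observed conversion probability is q = p(1 − s) + (1 − p)s.

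- p = .40, s = .10: q = .36 + .06 = .42, P = .33
- p = .40, s = .20: q = .32 + .12 = .44, P = .37
- p = .70, s = .10: q = .63 + .03 = .66, P = .82
- p = .70, s = .20: q = .56 + .06 = .62, P = .75

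The rule loses discrimination. The gap in pass probability between p = .70 and p = .40 is .874 − .290 = .584 with no misclassification. It is .816 − .329 = .487 at s = .10 and .748 − .371 = .377 at s = .20.

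**Step 3. Inactive drug.** With p = 0, only spurious conversion f is left. If it applies to all 7 pairs, P(X ≥ 4) is .003, .033 or .126 for f = .10, .20 or .30. If only some pairs are mismatched and f = .30 in those, P is 0 with 3 mismatched pairs, .008 with 4 and .031 with 5.

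**Step 4. Does any passage prevent a mismatch?** Section 10.2 could be read as meaning that only the primary is sampled. That reading conflicts with the node aspirate in Section 4.3, and it would mismatch every patient whose baseline was a node, whom Section 6.1 admits. A mismatch is therefore permitted on either reading.

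**The case against.** **Proportion.** This is a 7-patient exploratory pilot, and its rule decides only whether to study the drug further. Section 14 already tabulates each patient's values before and after treatment. A difference between specimens matters only if it crosses 30%. This stands, and it argues for a light remedy.

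**Size.** A reader might infer a much larger distortion by taking one direction at a time. Spurious conversion alone at .10, .20 or .30 lifts the pass probability at p = .40 from .29 to .41, .54 or .67; masking alone lowers it at p = .70 from .87 to .77, .63 or .48. The documents do not support a single direction or those rates. The fraction also applies to all patients: if half the pairs were mismatched, .30 overall would mean .60 within the mismatched pairs. Nor is an inactive drug likely to pass (Step 3).

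**Aspirates.** A reader might infer that an aspirate is never valid for the endpoint. Section 14 already replaces a patient whose material is inadequate for the stain, and nothing in the documents shows that an adequately processed aspirate reads differently from tissue. Barring aspirates would also narrow the low-risk office options in Section 4.3. What stands is that specimen type should be known and reported.

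**Residual tumour.** A reader might infer that patients could be dosed with no tumour left to sample. No passage says that the diagnostic biopsy removes the lesion. Definitive local-regional treatment is planned, Section 8.1 requires baseline examination and neck imaging, and a failure to obtain tissue leads to replacement. The inference is speculative and is not part of this point.

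None of these objections supplies a matching or recording rule.

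**Conclusion.** The concern holds. As written, the plan lets a site or specimen-type difference be scored as ribavirin inhibition, or hide it, and neither the analysis nor the listing would show that this had happened.

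The size is unknown because the documents give no concordance between node and primary or between aspirate and tissue. Under an assumed equal two-way error of .10 to .20 across all patients, the pass probability shifts by about .04 to .08 at p = .40 (upwards) and .06 to .13 at p = .70 (downwards). For an inactive drug it stays at or below .126 for spurious conversion up to .30 in every pair. This is a moderate loss of interpretability in the primary result. It is not evidence that the rule is likely to be met falsely, and the documents would not support that claim.

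**What to change.** **Sampling (Sections 4.3, 10.2 and 14).** State that the primary-endpoint post-treatment specimen comes from the same site class as the baseline, primary or node, whenever such tissue is available.

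- For resected patients, stain the block from the matching site.
- For research biopsies, sample the matching site, and prefer a tissue specimen where the investigator judges it feasible within the accessibility standard of Section 4.3.
- Where baseline tissue exists from both primary and node, stain both so that a match is possible.

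**Recording and reporting (Section 14).** Record site and specimen type for every specimen and add both to the per-patient table. Report the 4-of-7 count for all evaluable pairs and, separately, the count in matched pairs. Base any claim of inhibition on a result that also holds in the matched pairs. Unmatched patients stay in the study and in the listing.

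**Cost.** The change is protocol wording, two more columns in a table, and some extra baseline stains. There is slightly less freedom in choosing the specimen. A reader might infer that matching is only a choice of block for every surgical patient. It is not: a patient with a node baseline who has no neck dissection will have no node block and will remain unmatched. Sample size, threshold, treatment and surgical management do not change.
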